Pre-dose and between vials sampling: central blood sampling for pharmacodynamic biomarkers (dTT, ECT, aPTT, TT), pharmacokinetics (dabigatran and idarucizumab concentration) will occur immediately prior to administration of each vial of idarucizumab. Blood sampling for idarucizumab ADA will only occur prior to vial 1 administration.

Post-dose sampling: central blood sampling for pharmacodynamic biomarkers (dTT, ECT, aPTT, TT), pharmacokinetics (dabigatran and idarucizumab concentrations) will be collected at 30 minutes (\pm 10 minutes), 4 hours (\pm 30 minutes), 12 hours (\pm 1 hour) and 24 hours (\pm 2 hours) post-dose. Blood sampling for idarucizumab ADA will occur 30 days (+7 days) post-dose.

Blood sampling could be withheld or reduced per Investigator's judgement, e.g. if limited by blood volume, bleeding and/or distress considerations especially in very young children. E.g. omission of exploratory coagulation markers, reduced frequency of safety labs during the treatment period, etc.

Refer to appendix 10.3 for detailed information (priority order of lab parameters). The decision for reduced blood collection in those cases will be documented in the medical notes and CRF.

Time will be recorded for every blood sample taken.

Boehringer Ingelheim		4 February 2016
BI Trial No.: 1321.7		
c08884404-01	Trial Protocol	Page 7 of 77

⁸ Includes Haematology and Chemistry. Optional local blood draws for aPTT and other local lab testing may be done at the discretion of the treating physician to facilitate patient clinical management.

⁹ Local urine or other appropriate spot pregnancy test in female adolescents of child bearing potential (patients who have reached menarche). More frequent testing can be done if required by the local regulation and/or authority or per Investigator's judgement. Enrolment of pregnant patients is not allowed.

¹⁰ Re-start of anticoagulant therapy, if applicable, can be a return to dabigatran etexilate for patients from Group B. Patients from Group A have to be switched to a standard of care anticoagulant medication.

¹¹ Also needs to be completed if the patient withdraws prematurely following first vial of trial medication or at any later time point prior end of trial.

08884404-01Trial ProtocolPage 8 of 77Proprietary confidential information © 2016 Boehringer Ingelheim International GmbH or one or more of its affiliated companies

TABLE OF CONTENTS

TITLE PA	GE	1
CLINICA	L TRIAL PROTOCOL SYNOPSIS	2

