4.2.2 Restrictions

4.2.2.1 Restrictions regarding concomitant treatment

Prior treatment with the dabigatran reversal agent carries a theoretical risk of antiidarucizumab antibody formation, a possible immune reaction to the reversal agent and possible decrease of the efficacy of the reversal agent.

Administration of dabigatran etexilate to a bleeding patient or a patient requiring emergency surgery should be interrupted. There are no known restrictions on other drugs at this time.

Some idarucizumab may remain circulating for up to 24 hours after infusion (less than 1% of the dose in patients with normal renal function, but somewhat more in patients with renal insufficiency or failure). This may impact the expected efficacy of reinstituted anticoagulation with dabigatran.

In patients who stopped taking dabigatran etexilate due to an emergency surgery or other invasive procedure (Group B patients, refer to section 3.3.1), dabigatran etexilate treatment can be re-initiated 24 hours after administration of idarucizumab, if the patient is clinically stable and adequate haemostasis has been achieved. Re-initiation of dabigatran etexilate is not allowed in Group A patients.

If there is an urgent indication to re-start anticoagulation after trial treatment, the clinician must evaluate the risk-benefit ratio of doing so in the specific patient. The clinician may then choose to give one or more doses of a parenteral antithrombotic such as low molecular weight heparin as a bridging therapy at any time prior to re-initiation of dabigatran. In patients with creatinine clearance <30 mL/min dabigatran should not be re-started until the renal function has been corrected, or a longer term alternative anticoagulant should be chosen. Re-institution of anticoagulation is not a requirement of this trial, but is left to the discretion of the treating physician.

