6.2.3 Safety Follow-Up Period

Visit 3: 24-hour after dosing (+/- 2 hours)

Blood sampling could be withheld or reduced per Investigator's judgement, e.g. if limited by blood volume, bleeding and/or distress considerations especially in very young children.

Observations and procedures

- Draw blood 24 hours post-dose for central lab parameters (biomarkers and PK). Record time of blood draw.
- Draw blood 24 hours post-dose for local lab safety evaluation. Record time of blood draw.
- Bleeding assessment for the index bleed (Group A) or any unusual bleed associated with surgery (Group B). Bleeding assessment at or near time of blood draw.
- Surgery/procedure assessment at or near time of blood draw (Group B patients).
- Measure blood pressure and heart rate approximately hourly while the patient is in the emergency department (or similar department), then approximately every 6 to 8 hours for the next 72 hours or until patient is discharged, whichever comes first.
- Record adverse events
- Record concomitant therapies
- Re-start appropriate anticoagulant therapy (at treating physician/Investigator discretion)
- Optional (local) aPTT measurement or other local test

Page 54 of 77

Proprietary confidential information © 2016 Boehringer Ingelheim International GmbH or one or more of its affiliated companies

Visit 4: 7 days after dosing (+/- 3 days)

Observations and procedures

- Bleeding assessment for the index bleed (Group A) or any unusual bleed associated with surgery (Group B).
- Surgery/procedure assessment (Group B patients only).
- Measure blood pressure and heart rate (approximately hourly if the patient is still in the emergency or similar department, then approximately every 6 to 8 hours for the next 72 hours or until patient is discharged), whichever comes first.
- ECG
- Record adverse events
- Record concomitant therapies

Visit 5: End of Trial 30 days after dosing (+ 7 days)

Blood sampling could be withheld or reduced per Investigator's judgement, e.g. if limited by blood volume, bleeding and/or distress considerations especially in very young children.

Observations and procedures:

- Bleeding assessment for the index bleed (Group A) or any unusual bleed associated with surgery (Group B). Bleeding assessment at or near time of blood draw.
- Surgery/procedure assessment at or near time of blood draw (Group B patients only).
- Measure blood pressure and heart rate
- Draw blood for central lab parameters (ADA). Record time of blood draw.

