10.2 TIME SCHEDULE FOR BLOOD SAMPLING

Blood volumes to be collected for central lab parameters and local safety lab measurements will depend on available tube sizes and age of the patient as specified in Table 10.2: 1 and Table 10.2: 2. The sponsor may decide on other tubes sizes, if necessary. In such case total blood volume of the blood sampling may differ.

Cross reporting of lab results might be applied (across studies 1160.106, 1160.108 and this trial) in order not to increase the blood volume required for analysis.

Pre-dose and between vials sampling: central blood sampling for pharmacodynamic biomarkers (dTT, ECT, aPTT, TT), pharmacokinetics (dabigatran and idarucizumab concentration) will occur immediately prior to administration of each vial of idarucizumab. Blood sampling for idarucizumab ADA will only occur prior to vial 1 administration.

Post-dose sampling: central blood sampling for pharmacodynamic biomarkers (dTT, ECT, aPTT, TT), pharmacokinetics (dabigatran and idarucizumab concentrations) will be collected at 30 minutes (\pm 10 minutes), 4 hours (\pm 30 minutes), 12 hours (\pm 1 hour) and 24 hours (\pm 2 hours) post-dose. Blood sampling for idarucizumab ADA will occur 30 days (+7 days) post-dose.

In Table 10.2.: 1, general required blood volumes are indicated for age category < 6 years of age. For children < 6 years of age, available tube sizes for central lab parameters are 1.2 mL, and 2.7 mL EDTA monovettes and 1.4 mL Na Citrate monovettes. For all central lab parameters and local safety lab measurements about 29 to 37 mL blood will be required during the trial.

In Table 10.2.: 2, general required blood volumes are indicated for age category ≥ 6 years of age. For children ≥ 6 years of age, available tube sizes for central lab parameters are 3.0 mL

Boehringer Ingelheim		4 February 2016
BI Trial No.: 1321.7		
c08884404-01	Trial Protocol	Page 69 of 77
Proprietary confidential information ©	2016 Boehringer Ingelheim International GmbH or one of	or more of its affiliated companies

EDTA vacutainers and 2.7 mL Na Citrate vacutainers. For all central lab parameters and local

EDTA vacutainers and 2.7 mL Na Citrate vacutainers. For all central lab parameters and local safety lab measurements about 43 to 49 mL blood will be required during the trial.

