#### 7.5.2 Other Secondary endpoints

Percent change from baseline of coagulation tests (dTT and ECT) at 30 minutes post-dose will be summarized descriptively or listed only if deemed appropriate.

Reversal of the anticoagulant effect of dabigatran at time t is defined as:

$$Reversal (t) = \frac{predose coagulation test - postdose coagulation test at time t}{predose coagulation test - ULN} \times 100\%$$

Values equal to or higher than 100% will be interpreted as complete reversal of the anticoagulant effect. The reversal of anticoagulant activity will be based on central lab measurements and calculated for coagulation tests, dTT and ECT, separately. Reversal cannot be defined for patients with dTT or ECT pre-dose measurement value less than ULN; such patients are considered as not evaluable for reversal related endpoints. The ULN was determined by using data from studies 1321.1 and 1321.2, calculated as the (arithmetic) mean +2 \* standard deviation (SD) by using all data collected prior to the dosing of dabigatran and the data from patients who were on placebo, as well as pre-dose data from idarucizumab alone treatment (as available).

Time to achieve complete reversal will be reported by listing the calculated reversal values at planned time points and using flags to show whether complete reversal is achieved at planned time points.

Duration of complete reversal, defined as the time period from when a patient first achieves complete reversal, up to the earliest time point among the following: middle point between last observation of 100% reversal and subsequent observation, 24 hours post-dose or re-

starting the treatment of dabigatran or other anticoagulation. Duration of complete reversal can be defined only for those patients who achieved complete reversal.

For Group A patients only, the cessation of bleeding within 24 hours will be reported in a listing.

For Group A patients only, bleeding status will be assessed during treatment period and be summarized descriptively or listed only if deemed appropriate. Other clinical conditions that may contribute to bleeding (Group A patients only) during the trial, such as major trauma or the use of antiplatelets, will also be reported.

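### Group B: no visible text requires the 24-hour central sample to precede a dabigatran restart, and the SAP duration rule would accept a post-restart value

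*Protocol*

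**What the plan says.** Protocol 4.2.2.1 states for Group B that "dabigatran etexilate treatment can be re-initiated 24 hours after administration of idarucizumab, if the patient is clinically stable and adequate haemostasis has been achieved". Flow Chart footnote 10 agrees that a restart "can be a return to dabigatran etexilate for patients from Group B"; Group A must switch to another anticoagulant. Section 4.2.2.1 also lets the clinician give a parenteral antithrombotic as a bridge at any time before dabigatran is resumed.

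Protocol 6.2.3 sets the visit as "Visit 3: 24-hour after dosing (+/- 2 hours"). Its first listed procedure is "Draw blood 24 hours post-dose for central lab parameters (biomarkers and PK"). Near the end of the same list stands "Re-start appropriate anticoagulant therapy (at treating physician/Investigator discretion"). No sentence there, in the Flow Chart, in 4.2.2.1 or in appendices 10.2 and 10.3 ties the draw to the restart.

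For idarucizumab itself the order is explicit: appendix 10.2 says that central sampling "will occur immediately prior to administration of each vial of idarucizumab". Flow Chart footnote 7 adds "Time will be recorded for every blood sample taken".

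SAP 7.5.2 measures duration of complete reversal from its first occurrence to the earliest of "middle point between last observation of 100% reversal and subsequent observation, 24 hours post-dose", or the restart of dabigatran or another anticoagulant. It also lists reversal values by planned time, with flags for complete reversal. SAP 6.3 and 6.6 make a value non-evaluable when pre-dose or post-dose data are missing or the pre-dose result is below the ULN. Neither mentions restart.

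**The concern.** The endpoint describes how long idarucizumab keeps dabigatran reversed up to 24 hours. A sample taken after a new dabigatran dose can show two things at once: idarucizumab wearing off and fresh drug arriving. The SAP anticipates restart by ending the duration there, so no time after restart is credited. It does not stop a post-restart sample from serving as the next observation, which pulls the midpoint back to a time before the restart.

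The 24-hour value matters within this small dataset. It is in the second item of the priority order in appendix 10.3, and on the most reduced schedules it is one of only two post-dose biomarker values. Late loss of reversal is also a live question: protocol 1.1 reports that 93% of adults at 12 hours but 79% at 24 hours had unbound dabigatran below 20 ng/mL.

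**Working it through.** The plan gives no figure to reproduce, so the SAP rule is applied directly.

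**Inputs** (hours after the end of dosing, nominal times unless stated)
- Earliest dabigatran restart in Group B: R = 24 (protocol 4.2.2.1).
- 24-hour draw: y between 22 and 26 (protocol 6.2.3).
- Previous planned sample, full schedule: x = 12, window 11 to 13 (appendix 10.2).
- Previous planned sample, most reduced schedules, with no draw before vial 2 or at 4 or 12 hours: x = 0.5 (Tables 10.3: 2 and 10.3: 4).
- Assumed: first complete reversal at 0.5; complete reversal at x; the post-restart sample below 100%; no bridging anticoagulant.

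**Rule.** End of reversal = min[(x + y)/2, 24, R]. Duration = end − 0.5.

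**Step 1: is the sequence compliant?** Restart at 24 and draw at 24 + d, with d up to 26 − 24 = 2. Both are allowed.

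**Step 2: which limit governs?** For the midpoint not to come first with y = 26, (x + 26)/2 ≥ 24 is needed, so x ≥ 22. The preceding planned sample is no later than 13, so the midpoint governs. This holds only for a direct dabigatran restart. A bridging anticoagulant started before the midpoint would itself be the earliest limit.

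**Step 3: the derived end**
- Full schedule: (12 + 24 + d)/2 = 18 + d/2, so 18.0 to 19.0. For y = 26 with the 12-hour sample anywhere in its window: (11 + 26)/2 = 18.5 to (13 + 26)/2 = 19.5.
- Most reduced schedules: (0.5 + 24 + d)/2 = 12.25 + d/2, so 12.25 to 13.25.

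**Step 4: against a cut at 24 hours** (duration 24 − 0.5 = 23.5)

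| Schedule, draw at 26 h | Derived end | Duration | Shorter by |
|---|---|---|---|
| Full | 19.0 h | 18.5 h | 5.0 h |
| Most reduced | 13.25 h | 12.75 h | 10.75 h |

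At d = 0 the gaps would be 6.0 and 11.75 hours, but a new dose would have had no time to act, so d = 2 is the more relevant case.

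**Step 5: ordinary imprecision of the rule.** With no restart, a loss first seen at a 24-hour draw is dated to (12 + 24)/2 = 18, when the true end lies anywhere from 12 to 24 (±6). On the most reduced schedules it is dated to (0.5 + 24)/2 = 12.25, with a true end from 0.5 to 24 (±11.75). The shifts in step 4 are no larger than this. The problem is therefore one of cause, not of precision.

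**The case against.** The case for leaving the text alone is reasonable. The draw heads the Visit 3 list and is nominally at 24 hours, which is also the earliest dabigatran restart, so draw-first is the expected sequence. Several things must coincide for harm: a Group B patient evaluable for reversal, a restart soon after 24 hours, a late draw, the listed order reversed, and a fall below 100% within 2 hours. The documents give no absorption figure for that last step, and 4.2.2.1 notes that residual idarucizumab may weaken the new dose. The reduced-schedule figure is also less likely early on: the first patients are expected to be 12 to 18 years old, and the protocol's 45 kg example allows 94.5 mL over four weeks against 43 to 49 mL needed here.

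All of this limits the size of the point. It does not remove it. The Visit 3 list is not strictly chronological: vital-sign monitoring that can run for 72 hours stands ahead of the restart. The protocol states draw-before-dose elsewhere when it wants it.

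Visibility is partly covered. Sample times and concomitant therapies are recorded, the Flow Chart has a restart row, and SAP 7.5.2 needs the restart as an input. However, the source-data examples in protocol 8.3.1 name a start date for concomitant therapy, and a date cannot order two events at one visit. SAP 7.2 lists medication taken on treatment, which under SAP 6.1 ends one day after the last administration. The eCRF, the laboratory manual and the parent protocols are not available here and may settle the matter.

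Three stronger readings are tempting and not supported. A reader might infer that the 24-hour value is generally contaminated; the listed order points the other way. A reader might infer that the restart limit can never act; it also covers other anticoagulants, so earlier bridging can trigger it. A reader might infer that durations are understated by 5 to 11 hours; that assumes reversal was complete until 24 hours, which nothing measured between x and y shows. In the adult data quoted above, fewer patients were below 20 ng/mL at 24 hours than at 12, so a low 24-hour value need not come from a restart.

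**Conclusion.** The gap is real and small. A fully compliant sequence, with a direct dabigatran restart at 24 hours and a draw by 26 hours, lets the SAP date loss of reversal to about 18 to 19 hours (full schedule) or 12.25 to 13.25 hours (most reduced) on the strength of a sample taken after the new dose. The 24-hour flag can be affected in the same way.

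This rests on no earlier bridging, complete reversal at the preceding sample, and a post-restart result below 100%. If the new dose has not brought reversal below 100% by the draw, there is no effect. The frequency cannot be estimated from the documents. Only Group B and a descriptive secondary endpoint are involved, in about 5 patients; the primary safety endpoint is untouched and no testing is planned. It is a cheap improvement of low priority.

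**What to change.** 1. In protocol 6.2.3 and appendix 10.2, require the 24-hour central sample to be drawn before the first restarted dabigatran dose, within the existing 22 to 26 hour window, and have the clock time of that dose recorded.
2. In SAP 7.5.2, flag any sample drawn after the restart, and use it neither as the next observation in the duration rule nor for the 24-hour complete-reversal flag. It can still be listed.

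The cost is a short addition to the protocol and to the SAP, with no extra blood, visit or window. A site that wants to restart at exactly 24 hours must draw between 22 and 24 hours or hold the dose briefly. Where the order is not kept, the 24-hour value is lost from the derived endpoint. In the full-schedule example, the remaining limits of the present rule would then give 23.5 hours, while censoring at the last measured complete reversal would give at least 12 − 0.5 = 11.5 hours. Which of these is reported is the sponsor's choice, and the listing should make it clear.

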4.2.2.2 Restrictions on diet and life style

Not applicable.

4.2.2.3 Restrictions regarding women of childbearing potential

Female patients who are not of reproductive potential (i.e. pre-pubertal) are not considered to have childbearing potential and therefore do not need to use contraception to be eligible for the trial.

Female patients who have reached menarche are considered to have childbearing potential and must use acceptable method(s) of birth control as indicated in trial 1160.106 or 1160.108 wherein the patients are enrolled.

4.3 TREATMENT COMPLIANCE

The trial drug is administered as an intravenous injection/infusion in the emergency or similar department of the trial centre. The administrations start and stop times of the first and second injection/infusion for administration of the total dose will be recorded. Any interruptions or discontinuations of infusions will also be recorded. Refer to Section 4.1.4 for method of administration.
Page 37 of 77

Proprietary confidential information © 2016 Boehringer Ingelheim International GmbH or one or more of its affiliated companies

5 VARIABLES AND THEIR ASSESSMENT

5.1 TRIAL ENDPOINTS

5.1.1 Primary Endpoint

The primary endpoint is the safety of idarucizumab in a paediatric population as assessed by the occurrence of drug-related adverse events (including immune reactions) and all-cause mortality during the trial.

5.1.2 Secondary Endpoints

The reversal of anticoagulant activity and formation of antidrug antibodies (ADA) will be recorded in all patients (unless limited by blood volume, bleeding and/or distress considerations, especially in very young children).

Reversal of the anticoagulant effect of dabigatran at time t is defined as: ^a

Reversal (t) =
$$\frac{\text{predose coagulation test - postdose coagulation test at time }t}{\text{predose coagulation test - ULN}} \times 100\%$$

Values equal to or higher than 100% will be interpreted as complete reversal of the anticoagulant effect. The reversal of anticoagulant activity will be based on central lab measurements.

The following are the secondary endpoints:

- Percent change of coagulation tests (dTT, ECT) at 30 minutes post-dose compared to pre-dose.
- Time to achieve complete reversal of dabigatran effect^a, based on coagulation tests (dTT and ECT).
- Duration of complete reversal of dabigatran effect^a sustained at 24 hours post-dose, based on coagulation tests (dTT and ECT).
- Cessation of bleeding (Group A patients only).^b
- Bleeding status and other clinical conditions that may contribute to bleeding (Group A patients only) during the trial.^b
- Development of treatment-emergent ADA with cross reactivity to idarucizumab at 30 days post-dose of idarucizumab.^b
- ^a The ULN for each marker has been determined using data from idarucizumab phase I trials 1321.1 (U13-1773-01) and 1321.2 (c02742738). It was calculated as the (arithmetic) mean + 2*SD using all data collected prior to the dosing of dabigatran

and the data from patients who were on placebo as well as pre-dose data from idarucizumab alone treatment (as available). SD denotes the standard deviation.

^b This is a safety issue.

Page 39 of 77

Proprietary confidential information © 2016 Boehringer Ingelheim International GmbH or one or more of its affiliated companies

5.2 ASSESSMENT OF EFFICACY

The efficacy of idarucizumab will be assessed based on the central laboratory measurement of anticoagulant activity by dTT and ECT (secondary endpoints), aPTT and TT (further endpoints) tests. Further endpoints include the measurement of the unbound sum (free) plasma concentrations of dabigatran.

